4.0 Study Endpoints (if applicable)

Aim 1: Pre and post-test data collection, storage, and scoring calculations will be carried on by study coordinator/PhD student.

Pediatric Evaluation of Disability Computerized Adaptive Test (PEDI CAT) using a study iPad: The PEDI CAT measures 0 to 18-year-old children's abilities across three domains of mobility, selfcare and social function. It can be used with all pediatric diagnosis, across settings, and measures change following an intervention. It demonstrates excellent reliability⁴⁸, good validity^{49,50} with a minimal detectable change ranging between 2.2 to 3.3 across domains.⁵¹ Our study will measure only selfcare and mobility domains, which takes approximately 20 minutes to administer. Scaled (criteria referenced) and Standard (normative referenced) PEDI-CAT scores will be calculated.

6-Minute Walk Test (6MWT)

The 6MWT has demonstrated good reliability and validity in various pediatric populations.^{52,53} It has also been found to be predictive of cardiovascular fitness in survivors of children with pediatric cancers.⁵⁴ The 6MWT takes 6 minutes to administer.

Aim 2: Daily data collection by art and physical therapists during or after sessions, but data will be managed by study coordinator/PhD student following the sessions.

The Self-Assessment Manikin (SAM): The SAM is an image-based tool used to evaluate affective change in pleasure, arousal, and dominance in response to an object or event.⁵⁵⁻⁵⁷ (Appendix 6) Good reliability and validity of the SAM has been demonstrated.⁵⁸ Suggestions are that it perform similarly across diverse cultures and ages.⁵⁹⁻⁶¹ The SAM has been collected in studies involving exercise in which large

effect sizes were noted.⁶² We plan to use the computerized application of the SAM, which will take seconds to administer before and after daily AT and PT interventions.

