10.0 Study Design / Methods

Design: Randomized clinical trial to compare collaborative AT and PT to only PT in children undergoing HCT.

Using excel, the study coordinator will randomize each participant to either the PT and AT or PT only group. Each group will be assigned 10 participants.

Power

With a recruitment expectation of 30 participants, we expect a 30% drop out rate leaving 20 enrolled participants and feel confident that this study's aim 2 and 3 will be successfully powered to identify statistical significance ($p<0.05$) in outcomes. For Aims 2 and 3 which involve the collection of clustered data for HRV, SAM, and walking distance, in order to identify a medium effect, 80% or 90% power will be achieved with 61 or 82 measurement points respectively.^{54,55,66,67} Accounting for a dropout rate of 30%, the expected number of participants is 20. With 10 participants in the intervention group, 100 measurement points for HRV, SAM, and walking distance each are expected; thus, ensuring adequate power for aim 2 and 3.

For the PEDI CAT and 6MWT, to achieve 80% power, the projected sample size in each group is estimated to be 16 and 20; therefore, we proposed that we may not be adequately powered for aim 1.^{51,68} However, findings attributed to aim 1 will provide pilot data to inform a larger randomized control trial. Although aim 1 may not be adequately powered, the published minimal detectable change (MDC) for the PEDI CAT selfcare and mobility domains are 2.2 and 2.5 respectively while the Minimally Clinically Important Difference (MCID) for the 6MWT is 7%.^{69,70} Although, power to find a statistically significant difference may be inadequate, we expect to observe this level/magnitude of improvement in our proposed study. Variation values from this aim will provide data that are essential to guide future research.

Data Analyses

Aim 1: In children undergoing HCT during in-patient care, do a randomized group receiving a combination of Physical Therapy (PT) plus Art Therapy (AT) have improved functional activity level outcomes of self care and mobility as measured by the Pediatric Evaluation of Disability Inventory Computerized Adaptive Test and the 6-Minute Walk Test, compared with a group receiving PT only.

Hypothesis 1: Children receiving the combined intervention of PT plus AT will demonstrate greater improvements in self care and mobility skills.

Statistical Test: Independent sample t-tests

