Aim 2: Do children receiving PT plus AT have physiological (sympathetic or parasympathetic) and emotional responses to oil pastels and gouache as measured by respiratory sinus arrhythmia derived from heart rate variability and Self-Assessment Manikin scores during each of the daily AT sessions.

Hypothesis 2: Oil pastels or gouache AT will generate a RSA value in the direction of needed parasympathetic activity and balance the emotions of valence, arousal, and dominance.

Statistical Test: Repeated measures generalized linear regression

Aim 3: In children receiving PT plus AT, determine if there is a stronger association between the RSA values of oil pastels or gouache AT and an increased walking distance as measured by accelerometry during daily PT sessions.

Hypothesis 3: The media that best generates a parasympathetic RSA value and emotional balance will be associated with a greater walking distance.

Statistical Test: Repeated measures generalized linear regression

Data Collection

The 10-day intervention will begin on approximately Day 15 of HCT. Pre-test (Pediatric Evaluation of Disability Inventory and 6-Minute Walk Test) will be collected on Day 14. The same post-test data will be collected the day following the tenth day of intervention.

During the 10 days of intervention, the Self Assessment Manikin, heart rate variability, and walking distance will be collected daily.

The study coordinator will be responsible for storing all data. All documentation and data concerning each participant will be coded to protect confidentiality. All data collection and storage processes and locations will use study equipment (i.e., heart rate variability monitors, computers, College of Health Professions DA server) that is password protected, encrypted, and behind the MUSC firewall. All study related equipment will be locked in the office of the PI when not in use. There will be no transfer of data to a third party.

Procedures

- 1) IRB approval
- 2) Begin participant enrollment
- 3) Collaborate with HCT team to initiate recruitment and share study flyer
- 4) PI will obtain informed consent from participants in the hospital or electronically through MUSC secure email.
- 5) Randomize participant to AT and PT or PT only
- 6) Approximately Day 14 of HCT complete pre-test (Pediatric Evaluation of Disabilities Inventory and 6-Minute Walk Test)

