- 7) Day 15-24 of HCT: 45 minutes of AT and 30 minutes of PT OR 30 minutes of PT only. Heart rate variability, Self Assessment Manikin, accelerometry collected across sessions.
- 8) Approximately Day 25 of HCT complete post-test (Pediatric Evaluation of Disabilities Inventory and 6-Minute Walk Test)
- 9) Data analyses and dissemination.

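### Aim 1 names a t-test but not the score it is applied to; ANCOVA on the pre-test already collected is usually more precise at 10 per arm

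*Combined protocol and SAP*

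**What the plan says.** Under Data Analyses in Section 10.0, Aim 1 has a single line: "Statistical Test: Independent sample t-tests". The hypothesis above it is that "Children receiving the combined intervention of PT plus AT will demonstrate greater improvements in self care and mobility skills", which points towards change but defines no analysed variable.

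Both measures are taken twice. Under Data Collection, "Pre-test (Pediatric Evaluation of Disability Inventory and 6-Minute Walk Test) will be collected on Day 14"; under Procedures, "Approximately Day 25 of HCT complete post-test". Neither Section 4.0 nor Section 10.0 gives the pre-test a role in the analysis. For PEDI-CAT, Section 4.0 adds that "Scaled (criteria referenced) and Standard (normative referenced) PEDI-CAT scores will be calculated", without saying which is tested.

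The Power text in Section 10.0 assigns 10 participants to each group, says that for 80% power "the projected sample size in each group is estimated to be 16 and 20", and accepts that Aim 1 may be underpowered. It adds that "Variation values from this aim will provide data that are essential to guide future research".

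In the Procedures list, step 5 is "Randomize participant to AT and PT or PT only" and step 6 is the pre-test. Section 10.0 has the study coordinator randomise, and Section 4.0 has the study coordinator/PhD student collect and score the Aim 1 tests.

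**The concern.** The plan leaves open post-test or change scores for each measure, and Scaled or Standard scores for PEDI-CAT. Two analysts could follow it faithfully and report different results, and the choice could be made after the data are seen.

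A post-score t-test ignores the pre-test. A change-score t-test fixes the slope of post on pre at 1, and so over-corrects a chance baseline difference whenever the true slope is below 1. Which is more precise depends on a correlation the plan does not give. ANCOVA estimates the slope, so the choice need not be guessed.

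Aims 2 and 3 use only the combined-therapy arm, so Aim 1 is the only comparison that randomisation protects, and it is admittedly short of power. It is also meant to supply variability estimates for a larger trial. The post-score SD, change-score SD and residual SD are different quantities, and the plan does not say which it will deliver.

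**Working it through.** **Inputs.** From Section 10.0: n = 10 per arm; 80% power at 16 (PEDI-CAT) and 20 (6MWT) per group. Assumed: two-sided 0.05 (a 0.05 level is stated only for Aims 2 and 3, without sidedness); equal pre and post SDs; all 10 per arm analysed. No SD or pre-post correlation r is given, so r is varied.

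**1. The plan's own figure.** The 16 and 20 cannot be reproduced, because no difference, SD or sidedness is stated for Aim 1. They can be inverted. Solving P(T > t₀.₉₇₅) = 0.80, with T noncentral t on 2n−2 df and noncentrality d√(n/2), gives d = 1.024 at n = 16 and 0.909 at n = 20. The same effects at n = 10 give t-test power of 58.2% and 48.6%.

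**2. Variance of each estimator, relative to the post-score t-test.**
- Post-score: 1
- Change-score: 2(1−r)
- ANCOVA: (1−r²)(1 + 1/(2n−4)) = (1−r²) × 1.0625, where 1/16 is the expected cost of estimating the slope

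| r | Change | ANCOVA | ANCOVA ÷ change |
|---|---|---|---|
| 0.5 | 1.00 | 0.80 | 0.80 |
| 0.7 | 0.60 | 0.54 | 0.90 |
| 0.8 | 0.40 | 0.38 | 0.96 |
| 0.9 | 0.20 | 0.20 | 1.01 |

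Break-even points:
- Post against change: 2(1−r) = 1, so r = 0.5.
- ANCOVA against post: r = √(1 − 1/1.0625) = 0.24.
- ANCOVA against change: (1+r)/2 × 1.0625 = 1, so r = 2/1.0625 − 1 = 0.88.

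**3. Power at 10 per arm (PEDI-CAT/6MWT).** The plan does not say in which SD units its effect is expressed, so both readings are shown. ANCOVA power uses the noncentral t on 17 df, with variance (1−r²)(2/n)(1 + F/(2n−2)) averaged over F(1,18).

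(A) Effect in post-score SD units; the change-score effect is d/√(2(1−r)):

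| r | Post t | Change t | ANCOVA |
|---|---|---|---|
| 0.5 | 58%/49% | 58%/49% | 68%/58% |
| 0.7 | 58%/49% | 80%/70% | 83%/74% |
| 0.8 | 58%/49% | 93%/86% | 94%/87% |

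(B) Effect in change-score SD units; the post-score effect is d√(2(1−r)):

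| r | Post t | Change t | ANCOVA |
|---|---|---|---|
| 0.5 | 58%/49% | 58%/49% | 68%/58% |
| 0.7 | 39%/32% | 58%/49% | 62%/53% |
| 0.8 | 28%/23% | 58%/49% | 60%/50% |
| 0.9 | 16%/14% | 58%/49% | 58%/48% |

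Simulation of (A) with 100,000 trials per cell gave ANCOVA power of 0.676/0.577 at r = 0.5 and 0.834/0.740 at r = 0.7, against 0.678/0.576 and 0.834/0.741 from the formula. At the r values computed (0.3, 0.5, 0.7, 0.8, 0.9), ANCOVA is at most 0.5 point below the better t-test.

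**4. Chance baseline imbalance.** The baseline difference has SD √(2/10) = 0.447 in SD units. A difference beyond 0.5 SD in either direction therefore has probability P(|Z| > 0.5/0.447) = 0.26. At r = 0.7, an observed difference of 0.5 SD shifts the expected post-score difference by 0.5 × 0.7 = 0.35 SD, and the change-score difference by 0.5 × (1−0.7) = 0.15 SD the other way.

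**The case against.** The strongest reply is that the plan already leans towards change: the hypothesis speaks of improvement, and the Power text uses minimal detectable change values as benchmarks. Against a change-score t-test the gain is modest. It could be nil for Scaled PEDI-CAT scores or 6MWT distance, if the wide age range (up to 18 years) and the short gap between tests make r high. That is fair, and it means the large contrasts with a post-score t-test apply only to the less likely reading. It does not supply the missing definition or the unknown r.

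ANCOVA can also lose slightly outside the range computed. At r = 0 it has 55.5%/46.2% against 58.2%/48.6% for the post-score t-test. At r = 0.95, in change-score SD units, it has 56.6%/47.2% against 58.2%/48.6% for change scores. If only 7 per arm were analysed, the slope cost would be 1/(14−4) = 10% and break-even against change scores would fall to 2/1.1 − 1 = 0.82. These losses are at most about 4 points, small beside what a wrongly chosen t-test could lose.

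The effect sizes are inferred. One-sided at 0.05 they would be 0.90 and 0.80, with t-test power of 61%/53% at 10 per arm. The variance comparison in step 2 does not depend on them.

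Planning SDs could be reported whichever test is used, and Aim 1 is described as pilot data. Both are true, but the plan does not say which SDs it will report. The order of randomisation and pre-test is a separate matter of allocation knowledge. It is raised here because a baseline covariate should be measured before allocation is known.

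**Conclusion.** The concern holds. The Aim 1 analysis does not define its outcome variable, does not choose between PEDI-CAT score types, and gives the pre-test no stated role. This is a loss of precision and an open analytic choice, not bias, since either t-test is valid under randomisation.

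With equal SDs and 10 analysed per arm, ANCOVA has the smallest variance of the three analyses for r between about 0.24 and 0.88. Its power gain over a change-score t-test is about 9 to 10 points at r = 0.5, 4 at 0.7, 1 to 2 at 0.8, and nil from about 0.88. Over a post-score t-test the gain grows with r.

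ANCOVA does not guarantee 80% power. With the effect in post-score SD units, r must be about 0.7 for PEDI-CAT and higher for 6MWT. The power figures rest on back-solved two-sided effects and an unknown r, so confidence in their size is moderate. The specification gap is plain from the text. The change is recommended because it costs almost nothing.

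**What to change.** Replace the t-tests by ANCOVA: post-test score on arm and the pre-test score of the same measure, fitted separately for PEDI-CAT self-care, PEDI-CAT mobility and 6MWT. State whether Scaled or Standard PEDI-CAT scores are analysed. Report each adjusted difference with its 95% confidence interval, plus the residual SD and the pre-post correlation for planning the larger trial. If a t-test is kept as a sensitivity analysis, say whether it uses post-test or change scores. If ANCOVA is declined, the outcome variable and score type still need naming.

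Complete the pre-test before allocation is revealed by exchanging steps 5 and 6 of the Procedures. The planned days allow this: the pre-test is on Day 14 and the intervention starts on about Day 15.

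The cost is one line of analysis text, one degree of freedom, and about 6% of variance (1/16) for estimating the slope. No new data or visit is needed.

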9.0 Consent Process

Informed consent will be sought upon each child's admission to MUSC Shawn Jenkins Children's Hospital. It will occur approximately on or before Day 13 of the HCT. Day 14 will be for pre-testing and day 15 for start of intervention. Children's authorized representative will have at least 24 hours prior to study intervention initiation.

Consent may be obtained in person at the hospital or using an electronic consent.

For in person consents, the PI will obtain informed consent from parents or legal guardians at the MUSC Shawn Jenkins Children's Hospital.

The PI will communicate by phone or email with the parent or legal guardian to establish a time to seek informed consent at the hospital OR discuss the use of an electronic consent. If an electronic consent is used, the PI will email the consent to the parent or legal guardian using secure MUSC email. Then the PI will contact the parent or legal guardian by phone to review the informed consent and answer any questions. If the parent or legal guardian wishes to enroll in the study, they will sign the informed consent and return to the PI through the MUSC email system.

Assent will be obtained from each individual child or adolescent at the same time that the informed consent is obtained from parents. If informed consent is carried out electronically, the parent will be asked to document the child or adolescent's assent using MUSC email communication.

If a child withdraws assent prior to a study session, parents will be notified. If the child withdraws assent for a session for 3 days in a row, the child will be withdrawn from the study. If assent is less than 3 days, then missed days will be added to the study duration until 10 days are completed.

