12.0 Data Management

All documentation and data concerning each participant will be coded to protect confidentiality. All data collection and storage processes and locations will use study equipment (i.e., heart rate variability monitors, computers, College of Health Professions DA server) that is password protected, encrypted, and behind the MUSC firewall. All study related equipment will be locked in the office of the PI when not in use. There will be no transfer of data to a third party.

13.0 Provisions to Monitor the Data to Ensure the Safety of Subjects (if applicable)

All documentation and data concerning each participant will be coded to protect confidentiality. All data collection and storage processes and locations will use study equipment (i.e., heart rate variability monitors, computers, College of Health professions DA server) that is password protected, encrypted, and behind the MUSC firewall. All study related equipment will be locked in the office of the PI when not in use. There will be no transfer of data to a third party.

Children undergoing HCT will experience symptoms related to the HCT and may experience additional medical complications. Our study involving art and physical therapy interventions will only be carried out during the in-patient phase, which will be helpful when considering adverse effects because a variety of

healthcare professionals will be at hand to possibly prevent and ameliorate any adverse events. For example, prior to each daily session, the art and/or physical therapist will ask the child's nurse if the patient is medical stable to participate. If the nurse, reports that the child is not medically stable, then the child's session will be postponed until stable.

Common symptoms following transplant include fatigue and deconditioning which is associated with lower strength and endurance. We believe children' participation in this study will lead to temporary reports of elevations in fatigue, weakness, and poorer endurance symptoms; however, we will not view these as adverse events since these symptoms are also common to increases in activity level that will be generated by art and physical therapy.

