Unanticipated adverse events that might be possible are falls secondary to possibly osteostatic hypotension or clumsiness. If an unanticipated event were to occur, the intervention therapists would immediately report the incident to the child's nurse and attending physician so that appropriate assessment and treatment can begin. The intervention therapist would then report the event to the PI, who would contact the IRB and complete an adverse event report. To avoid experiencing an adverse event, before each intervention session, study team members will communicate with each child's nurse concerning child's medical status that day. If nursing agrees the child's statue is stable, the intervention will proceed. If nursing reports that the child's status is not stable, the intervention will be postponed. If the child experiences a change in medical status that requires transferred to a more complicated medical environment, such as the ICU, study intervention will be postponed until return to the HCT unit. If a child's medical status improves and they are transferred to a "regular" hospital room, the study intervention will continue. Once the child is discharge to home, the study intervention will be stopped even if 10 days of the study intervention have not been provided.

We consider this study to be low risk however our data and safety monitoring plan will be continuous, close monitoring by the study investigator/co-investigators of all participants. The PI ([name]) and Co-I's ([name]) will meet once a month discuss data and safety monitoring. During these meetings we will look for any negative trends in the data we have collected (Self Assessment Manikin, PEDI, 6-Minute Walk Test, heart rate variability, accelerometry) that could indicate adverse events and provide a timely summary report of adverse events to the IRB.

Any reportable safety events that are unexpected, serious or may be related to the subjects' participation in this research will be reported to the MUSC IRB and NEA in accordance with their policies.

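### Aim 1 has no planned post-test for a child discharged home before session ten; do the two tests before discharge

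*Combined protocol and SAP*

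**What the plan says.** - **Timing of the post-test.** Section 10.0, Data Collection: "The same post-test data will be collected the day following the tenth day of intervention". Step 8 of the Procedures in the same section gives a nominal day: "Approximately Day 25 of HCT complete post-test (Pediatric Evaluation of Disabilities Inventory and 6-Minute Walk Test". Step 7 places the sessions on Days 15 to 24, so Day 25 is the day after a ten-day run with no gaps.
- **Discharge.** Section 13.0 says that once the child goes home "the study intervention will be stopped even if 10 days of the study intervention have not been provided". A move to an ordinary ward does not stop it.
- **Slippage.** If the child is not medically stable, "then the child's session will be postponed until stable". During an ICU stay, "study intervention will be postponed until return to the HCT unit". For fewer than three days of refusal, Section 9.0 says "then missed days will be added to the study duration until 10 days are completed".
- **Withdrawal.** Section 9.0: "If the child withdraws assent for a session for 3 days in a row, the child will be withdrawn from the study". Section 14.0, on withdrawal, is marked as not applicable.
- **Analysis.** Section 10.0 names independent-sample t-tests for Aim 1. It gives no rule for a child without a post-test.

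**The concern.** The test is scheduled by a milestone, session ten, that the plan itself expects some children not to reach. Each postponed or added session moves that milestone later, while the discharge date need not move with it, so discharge can come first.

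Aim 1 is the only comparison of the two randomised arms; Aims 2 and 3 concern the combined-therapy arm alone. The Procedures randomise (step 5) before the pre-test (step 6), so a lost post-test is a loss after randomisation. The time of discharge is plausibly related to recovery, which is close to what the PEDI CAT and 6MWT measure. If children who go home early are not tested, the arm difference and the variation estimates that the Power section wants for a later trial would describe only those who stayed. An outcome not collected before discharge may not be recoverable.

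**Working it through.** **1. Which children have a planned test time**

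| Child's course | Post-test time in the plan |
|---|---|
| Completes ten sessions in hospital | Day after session ten |
| In hospital around Day 25, sessions postponed | Nominal Day 25 or the day after session ten; the two now differ and no latest day is set |
| Discharged home before session ten | None: session ten never occurs, and no discharge test or return visit is described |
| Withdrawn after three refused days in a row | None: the child has left the study |

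The third row is the point made here.

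**2. The plan's own attrition figure**

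The Power section says "we expect a 30% drop out rate leaving 20 enrolled participants", starting from 30 recruited.

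- Forward: 30 × (1 − 0.30) = 21, against 20 stated.
- In reverse: 20 / (1 − 0.30) = 28.6, rounded up to 29, against 30 stated.

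The figure is reproduced to within one child, and the 20 is already net of dropout. The same section then counts 10 children × 10 sessions = 100 measurement points in the combined arm. So no further allowance is made for incomplete courses among the 20, although Section 13.0 provides for them.

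**3. Precision, for assumed losses**

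The documents do not say how many children go home before session ten. The losses below are assumptions, split equally between arms. The 95% interval half-width in SD units is t(0.975, 2n − 2) × √(2/n), with n per arm.

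The Power section gives 16 and 20 per group for 80% power, taken here as PEDI CAT and 6MWT in that order. It gives no SD or planned difference, so these cannot be reproduced directly. Solving back with a two-sided 0.05 t-test (assumed for Aim 1) gives standardised differences of 1.02 and 0.91, which supply the power columns.

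| Missing of 20 (assumed) | n per arm | Half-width | Power, PEDI CAT | Power, 6MWT |
|---|---|---|---|---|
| 0 | 10 | 2.101 × 0.447 = 0.94 SD | 58% | 49% |
| 2 | 9 | 2.120 × 0.471 = 1.00 SD | 53% | 44% |
| 4 | 8 | 2.145 × 0.500 = 1.07 SD | 48% | 40% |

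The fix keeps the trial nearer the first row. It does not bring Aim 1 to 80% power.

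**4. Bias**

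Suppose k of the 10 children in an arm lack a post-test and their mean outcome would have differed by δ from that of the others. The full arm mean is the observed mean plus (k/10) × δ. The error in the arm difference (combined minus PT only) is then (k_PT × δ_PT − k_comb × δ_comb)/10. It is zero if loss is alike in both arms and can take either sign otherwise. The documents give neither k nor δ, so no size or direction follows.

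**5. Calendar (wording note)**

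Section 3.0 says that sessions run Monday to Friday. With Day 15 falling on Monday through Sunday in turn, and no session missed, the tenth session falls on Day 26, 28, 28, 28, 28, 28 or 27. The next-day test is on Day 27 to 29, two to four days after the nominal Day 25. It falls on a Saturday for three of the seven start days (Monday, Saturday, Sunday).

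**The case against.** The strongest reply is that the plan is silent rather than exclusive. Section 13.0 stops the intervention at discharge, not the assessment, and step 8 gives an approximate Day 25 without requiring ten sessions or inpatient status. Staff might test a child on the way out, or ask the family back. This stands to a degree: it cannot be said that these children would certainly contribute no outcome. But Aim 1 is framed as inpatient, the only setting named is the hospital, no visit after discharge is described, and Day 25 is simply the day after Days 15 to 24. What remains is that no test is provided for, and unwritten practice could vary between children.

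The plan also calls Aim 1 underpowered and treats it as pilot data. That is fair and limits what is at stake for power, but pilot estimates of variation suffer from selective loss too.

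Three stronger readings are tempting and not supported:

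- **That 30% of the 20 randomised, or 6 children, could lack a post-test.** The Power section has already taken the 30% off to arrive at 20; applying it again deducts it twice.
- **That children withdrawn after three refused days show the same gap.** They have left the study under Section 9.0. Having no post-test is the ordinary result, and a test before discharge would not by itself reach them.
- **That the date mismatch is itself a defect in the comparison.** The start and post-test days are both given as approximate.

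**Conclusion.** The concern holds for children discharged home before session ten. The plan ties the Aim 1 post-test to a session they never have and offers no other occasion, so they may drop out of the only randomised comparison.

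The number affected and the direction of any bias cannot be determined; the harm could range from nil to material. The gap itself is a matter of text and depends on no assumed figure. The precision and power values above rest on assumed losses, an equal split between arms, and effect sizes solved back from the plan's 16 and 20 per group.

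The main gain from the change is having outcomes on early leavers, not power. It is worth making because the loss is foreseeable and largely avoidable. The calendar and Section 14.0 points are matters of wording only.

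**What to change.** In Section 10.0, set the PEDI CAT and 6MWT for the day after session ten or, if discharge home comes first, before discharge. State a latest test day for children who remain in hospital with postponed sessions, and test on that day even if fewer than ten sessions have been given. If the Monday-to-Friday schedule stays, that day should be no earlier than Day 29, the latest next-day test with no session missed.

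Record the number of sessions received and the days since the pre-test. Analyse every child with a post-test in the arm to which they were randomised, and report missing post-tests by arm with reasons. A child withdrawn after three refused days would be tested only if the child and parent agree.

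Wording: align the day numbers with the weekday schedule, say what happens when the test falls on a Saturday, and have Section 14.0 refer to the withdrawal rule in Section 9.0.

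The cost is small. These are the same two tests, once per child after treatment, at 20 + 6 = 26 minutes by the plan's own figures. Staff need notice of discharge. The downside is that some children are tested after fewer sessions and at varying intervals from the pre-test, which may add variation; that is why both are recorded. When treatment is given or stopped does not change.
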